## **12 PHARMACOKINETIC ANALYSIS**

Due to the sparse PK data collected from individual participants, non-compartmental analysis will not be performed.

Descriptive statistics of the concentration data will be summarized based on nominal timepoints by treatment and will be presented in a table using the PK set. PK concentration data, including actual sampling time, will be provided in a listing. For computation of mean plasma concentrations, data that are below the limit of quantification will be set to the limit of quantification.

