1	30	ASN008 5.0% BID topical application applied as a thin layer (approximately 2 mg/cm ²) for 4 weeks (28 days)
2	30	ASN008 2.5% BID topical application applied as a thin layer (approximately 2 mg/cm ²) for 4 weeks (28 days)
3	30	ASN008 1.25% BID daily topical application applied as a thin layer (approximately 2 mg/cm ²) for 4 weeks (28 days)
4	30	ASN008 matching vehicle BID topical application applied as a thin layer (approximately 2 mg/cm ²) for 4 weeks (28 days)

N=number of participants; BID=twice daily.

Participants will be randomized to receive ASN008 gel 1.25%, 2.5%, 5% or matching vehicle applied BID to the AD lesions as instructed for a treatment period of 4 weeks (28 days). The first dose will be applied on Day 1 and the last dose will be applied during the Day 28 study visit; participants are not to receive study treatment for more than 28 days.

Safety monitoring: Adverse events will be coded according to the latest version of the Medical Dictionary for Regulatory Activities (Version 25.1 or later). All safety data (scheduled and unscheduled) will be presented in data listings.

Safety will be assessed by collecting TEAEs, recording vital signs, performing complete and brief physical examinations, ECGs, and evaluating clinical laboratory results and local tolerability assessments.

Any safety concerns arising during the study will be evaluated by the Medical Monitor and Sponsor to determine the appropriate course of action (e.g., treatment discontinuation, stopping enrollment) for the remaining participants and communicated to the sites, if needed.

Participation in the PK part of the study is mandatory. Blood samples will be collected as follows:

- Day 1: Pre-dose (0), 1, 2, and 4 hours post-dose.
- Day 28: Pre-dose (0), 1, 2, and 4 hours post-dose.

Inclusion/Exclusion Criteria:**Inclusion criteria:**

Participants are eligible to be included in the trial if ALL the following criteria apply:

1. Male or female participants, 18 years or older, at the time of informed consent.
2. Diagnosis of mild to moderate AD for at least 12 months according to American Academy of Dermatology Consensus Criteria with no significant disease flares for at least 4 weeks before Screening (based upon medical chart, treating physician, or participant report with documented clinical confirmation by the Investigator).
3. vIGA score of 2 or 3 at Screening and Day 1.
4. BSA $\leq 20\%$ at Screening and Day 1.
5. NRS ≥ 7 at Screening and Day 1.

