1. INTRODUCTION

ASN008 is formulated as a topical gel with minimal systemic exposure intended for twice daily (BID) topical application. It is a sodium channel blocker, and like other known neuronal sodium channel blockers, is believed to block the sodium channel by binding to an intracellular channel site. Because ASN008 is a permanently charged quaternary amine, it cannot gain efficient entry into the interior of the cell via passive permeation through the cell membrane, however, ASN008 does gain entry into cells through open Transient Receptor Potential (TRP)-V1 and TRPA1 channels. These channels are opened by a variety of stimuli, including heat, acidic pH, and exposure to any number of irritants or inflammatory mediators such as those involved in many pathological conditions that have associated acute or chronic itch. The transmission of such itch signals is mediated through sodium channels in afferent C and A δ nerve fibers. Furthermore, TRPV1 and TRPA1 channels are selectively expressed in C and A δ fibers of sensory afferent neurons but are not found in motor neurons. Because of this selective expression pattern, ASN008 is capable of sensory nerve type selective blockade of sodium channel signaling, making it an inviting strategy for developing a selective and well tolerated therapy for pruritus.

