Assessment of the 5% gel as the top dose in this Phase 2 dose-response study is justified based on 1) negligible systemic exposure, safety and tolerability in humans in the Phase 1/1b study; 2) high systemic safety margin based on lack of adverse finding after IV and topical administration in rats and minipigs, respectively; and 3) an application rate in $\mu\text{g}/\text{cm}^2$ that is lower than that at dermal no observed adverse effects level in minipigs after topical administration at lower than application rates previously evaluated in the Phase 1/1b study. Additional details regarding completed clinical and nonclinical studies can be found in the Investigator's Brochure (IB).

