9.3.2. Pharmacokinetic Analyses

ASN008 concentration data and PK parameters will be summarized per cohort based on nominal timepoints using descriptive statistics, such as mean, SD, geometric mean, CV%, median, minimum and maximum. PK parameters (apparent systemic clearance [CL/F], apparent volume of distribution [Vd/F], and distribution clearance) will be calculated using population-based methods (e.g., Nonlinear Mixed Effects Modeling) appropriate for sparse samples. Measures of inter- and intra-individual variability will be estimated.

PK-safety and efficacy relationships may be explored using linear regression, loess plots, Hills functions, or logistic regression, as appropriate.

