### 5.4 Descriptive Statistics

All continuous variables will be summarized by the number of participants, mean, SD, median, minimum, and maximum. Categorical variables will be presented as frequencies and percentages. Summary tables will be presented by treatment and visit, when applicable.

- Change from baseline will be calculated as:
  - Assessment value at post-baseline visit X – baseline value.
- Percent change from baseline will be calculated as:
  - $(\text{Assessment value at post-baseline visit X} - \text{baseline value}) / \text{baseline value} \times 100$ .

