## **6 STATISTICAL CONSIDERATIONS**

### **6.1 General Statistical Considerations**

The significance level for this trial is set to be 2-sided 0.05 unless otherwise specified. For PK data, geometric mean and percent of coefficient of variance (%CV) will be presented.

All decimal places will be kept to 3 places or less.

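### SAP 12 substitutes the limit of quantification for every below-limit concentration when means are computed, with no Day 1 pre-dose exception and no required below-limit count, so a wholly below-limit pre-dose cell prints a mean equal to the limit

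*SAP*

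**What the plan says.** SAP section 12 drops non-compartmental analysis because sampling is sparse. It plans a table of concentrations by nominal time and treatment on the PK set, with this rule: "For computation of mean plasma concentrations, data that are below the limit of quantification will be set to the limit of quantification". It adds that "PK concentration data, including actual sampling time, will be provided in a listing".

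The statistics for that table are named in three places:
- Protocol 9.3.2 has concentrations "summarized per cohort based on nominal timepoints using descriptive statistics, such as mean, SD, geometric mean, CV%, median, minimum and maximum".
- SAP 5.4: "All continuous variables will be summarized by the number of participants, mean, SD, median, minimum, and maximum".
- SAP 6.1: "For PK data, geometric mean and percent of coefficient of variance (%CV) will be presented".

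None of these is a count or percentage of BLQ values. Protocol 9.3.2 gives no BLQ rule, and SAP section 15 lists no change on the point.

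The Day 1 schedule in the protocol synopsis is "Day 1: Pre-dose (0), 1, 2, and 4 hours post-dose", and protocol 3.1 puts the first dose on Day 1. The PK set (SAP 4.4) is defined by having been dosed and having ASN008 concentration data. It does not exclude vehicle participants.

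On expected levels, the protocol introduction says that "ASN008 is formulated as a topical gel with minimal systemic exposure", and protocol 1.1 supports the top strength partly by "negligible systemic exposure, safety and tolerability in humans in the Phase 1/1b study".

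**The concern.** Substituting the limit gives an upper bound on a mean when drug may be present at an unmeasurable level. A sample taken before the first application is different, because the expected concentration is zero. Applied literally, the rule puts a positive number there. The same number can appear after dosing in an arm with no measurable drug, and nothing in the text requires a count that would tell the reader how much of a mean is substituted.

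The rule also names means only. Whether it extends to SD, geometric mean and CV% is not stated, so two programmers could produce different tables from the same data.

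At stake is the reading of the only PK summary table that SAP 12 specifies, for a product whose low systemic exposure is part of the case for its top strength.

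**Working it through.** The documents state no figure to reproduce here, and they give neither the limit of quantification nor a BLQ rate. Results are therefore in units of the limit, L.

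**1. Wholly BLQ cell.** With k of n values BLQ, the SAP mean is [k x L + sum of quantifiable values] / n. With k = n this is nL / n = 1.00 L for any n. For a planned cohort of 30, all BLQ:

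| BLQ set to | Mean |
|---|---|
| L (SAP rule) | 1.00 L |
| L/2 | 0.50 L |
| 0 | 0 |

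If the substitution also fed the other statistics, which SAP 12 does not say, the first row would have geometric mean 1.00 L, SD 0 and CV 0%.

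**2. Number of cells.** Two days x 4 nominal times x 3 strengths = 24 active-arm cells. Day 1 pre-dose accounts for 1 x 3 = 3 of them. Vehicle cells are added only if vehicle is tabulated.

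**3. Post-dose cells (assumption: lognormal concentrations, CV 50, 100 or 150%).** Set L = 1 and let p be the BLQ proportion.
- Log-SD: s = sqrt(ln(1 + CV²)).
- Log-mean: mu = -s x z(p), so that P(X < L) = p.
- True mean: M = exp(mu + s²/2).
- Mean under the SAP rule: M x Phi((mu + s²)/s) + L x p.
- Overstatement: SAP mean / M - 1.

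Example, CV 100% and p = 0.50: s = sqrt(ln 2) = 0.833, mu = 0 and M = exp(0.347) = 1.414. The SAP mean is 1.414 x Phi(0.833) + 0.50 = 1.414 x 0.797 + 0.50 = 1.628. The overstatement is 1.628/1.414 - 1 = 15.1%.

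| BLQ | CV 50% | CV 100% | CV 150% |
|---|---|---|---|
| 10% | 0.9% | 0.7% | 0.5% |
| 25% | 3.7% | 3.5% | 2.7% |
| 50% | 12.9% | 15.1% | 13.9% |
| 75% | 34.2% | 49.3% | 52.5% |
| 90% | 68.4% | 117.6% | 142.9% |

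**4. Can a reader tell a mostly BLQ cell from a wholly BLQ one?** At 90% BLQ the SAP mean is 1.03 / 1.06 / 1.09 L for the three CVs, close to the 1.00 L of a wholly BLQ cell, so the mean hardly separates them. The maximum usually does. With n = 30, the chance that no value exceeds L is 0.9^30 = 0.042, so in about 96% of such cells the maximum is above L. Its median, exp(mu + s x z(0.5^(1/30))), is about 1.4 / 1.8 / 2.2 L.

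**The case against.** The case for leaving the rule alone has real weight. It is prespecified and stated openly, no other passage contradicts it, and it can only overstate exposure, which works against the sponsor's own description of the product. Limit, half-limit or zero is largely a matter of convention. The PK endpoints are population CL/F and Vd/F and their variability. No test, dose-selection rule or efficacy analysis in the documents uses these means. A pre-dose mean equal to the limit is unlikely to be read as true exposure, and the maximum and the individual listing help to expose it.

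Most of that stands, and it keeps the point small. It does not rescue the Day 1 pre-dose cell, where an upper bound on exposure serves no purpose. The mitigation is also partial: SAP 12 does not say how BLQ values enter the median, minimum or maximum, and does not require them to be flagged in the listing.

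A further objection is to the obvious remedy. Setting pre-dose values to 0 while keeping the limit after dosing would print 0, L, L, L in an arm that is BLQ throughout, an apparent rise with no measurable drug. The present rule prints a flat L, L, L, L. That objection is correct, and the fix below avoids the step.

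A reader might infer more than the documents support:
- That post-dose means will be badly inflated. No BLQ rate is given, and below about 25% BLQ the effect is negligible under the assumptions used.
- That a BLQ count is the only way to recognise a wholly BLQ cell. The maximum usually does so too.
- That the output will lack a count. No table shell is in the documents; the supportable statement is that the text does not require one.

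**Conclusion.** The point holds as a minor one, confined to the descriptive concentration table. The firm part needs only the SAP's own rule: a wholly BLQ Day 1 pre-dose cell, expected in 3 of 24 active-arm cells because no trial drug has yet been applied, prints a mean of 1.00 x the limit where the expected value is zero. This is a stated rule that gives a wrong value, rather than a detail left open.

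The post-dose part is conditional. With lognormal concentrations and CV 50-150%, means are overstated by under 4% at 25% BLQ, about 13-15% at 50% and 34-53% at 75%. The documents do not show where in that range the trial would fall. The direction is always towards more exposure.

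It would be tempting to read this as bias in the population PK estimates or the efficacy results. The documents do not support that: the rule is written for mean concentrations, and nothing links those means to either analysis.

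**What to change.** In SAP section 12:

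1. Report n (%) BLQ for every nominal time and treatment.
2. Where all values in a cell are BLQ, as expected at Day 1 pre-dose and in vehicle if tabulated, print the mean as BLQ, with geometric mean and CV% marked as not calculated. Apply this to every cell alike, so that no artificial step from 0 to the limit appears after dosing or between arms.
3. State which statistics the substitution covers. If the limit is kept in partly BLQ cells, label those means as upper bounds.

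If Day 1 pre-dose BLQ values are instead set to 0 while post-dose values stay at the limit, the table should carry a note that an arm BLQ throughout would show an apparent rise from 0 to the limit.

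The cost is a few sentences, slightly more table programming and some cells without a numeric mean. No new data are needed.

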## 13 EFFICACY ANALYSIS

Efficacy analysis will be performed on the modified intent-to-treat set and per protocol set; the modified intent-to-treat set will be used as the primary analysis set.

### 13.1 Primary Efficacy Endpoint

The aims of the analyses of the primary endpoint, percent change from baseline at Week 4 in daily peak pruritus NRS, are to test for treatment effect; to characterize the gel concentration-response curve; to estimate the minimum effective and optimal concentration. The MCPMod approach will be applied for this study. If any candidate model given below is significant, the significant treatment effect will be concluded, then the significant models will be used to estimate the minimum and optimal concentration.

In essence, the aim of the primary analysis is to establish the ASN008 gel concentration-response curve, the response is defined as the change from baseline in 7-day average of the daily peak pruritus NRS at Week 4 for mild and moderate atopic dermatitis participants who do not use any prohibited medications during the entire study and have no safety concerns. For the primary analysis, any data after use of the prohibited medication will set to missing values. The missing data will be imputed implicitly using MMRM modeling under assumption of missing at random.

For the MCPMod approach, the candidate gel concentration-response models to be applied are given follows:

[figure not shown]
- Linear model.
- Quadratic model with maximum effect reached at 3.5%, the model parameter is - 0.1428571.
- Exponential model which reaches 20% of the effects at 2.5%, the model parameter is 1.803368.
- $E_{max}$  model with  $ED50 = 2.5\%$ .
- Sigmoid  $E_{max}$  model with  $ED50=2.5\%$  and Hill's parameter = 2.5.
- Logistic model which reaches 20% and 95% effects at concentrations 2.5% and 5%, respectively, the model parameters are  $ED50\% = 3.3002654$ ,  $\delta = 0.5772694$ .

The minimum effective concentration is defined as the lowest concentration whose standardized effect size is at least 0.25 and is significantly different from placebo at a 2-sided significance level of 0.2.

The optimal concentration is defined as the highest concentration of ASN008 used in this clinical trial without safety concerns for linear and exponential models, or the lowest concentration which maintains 90% of the maximum effect for the rest of candidate models.

Figure 2 depicts the shapes of curves for each candidate model, assuming the vehicle effect is 10% and treatment effect is 40% (30% improvement over vehicle).

Figure 2 Candidate Concentration - Response Models

Analysis of primary endpoint consists of the following steps:

Mean and variance estimation: A MMRM model with visit, treatment and visit by treatment interaction as fixed effects, baseline NRS as covariate, participant as random effects will be fitted first, the ls means and their variance-covariance matrix at Week 4 will be estimated using the fitted model.

1. MCP-step: the candidate models are tested using the estimated means and their variance- covariance matrix from the previous step. If any of the models is statistically significant at two-sided significance level of 0.1, the treatment effect is established, the analysis moves to the next step.
2. Mod-step: the concentration-response curve will be characterized, and the minimum effective concentration and optimal concentration will be estimated. All significant models indicated by the previous step will be fitted, and minimum effective concentration and optimal concentration will be estimated based on the fitted models.
3. Finally, weighted estimates for minimum effective concentration and optimal concentration will be calculated using weighing in Buckland et al. (Buckland 1997).

For MMRM model fitting, the unstructured (UN) variance-covariance matrix will initially be assumed. If the model does not converge using the UN covariance structure, the autoregressive (order 1) AR(1) structure will be used. If the AR(1) structure also does not converge, other covariance structures, such as the Toeplitz structure, deemed appropriate to fit the data will be used.

To estimate the degree of freedom, the Kenward Roger method will be used.

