5.6. Blinding

This trial will be double-blinded. At all times, treatment and randomization information will be kept confidential and will not be released to the Sponsor's trial team until database lock is completed and all safety data has been cleaned and monitored. Investigators, participants, and clinical staff will remain blinded throughout the trial.

Blinding codes should only be broken in emergency situations for reasons of participant safety. If unblinding the treatment assignment for a participant is necessary due to a medical emergency (an unexpected serious adverse event [SAE] per product's safety profile) and other significant

medical situations such as pregnancy, the Investigator can make the decision to unblind the treatment assignment if knowing the treatment assignment will help the treatment decision of the particular AE. When the blind for a participant has been broken, the reason must be fully documented in the source document and eCRF. Whenever possible, the Investigator should contact the Sponsor or its designee before breaking the blind. If the blind is broken, the Investigator should promptly inform the medical monitor. Documentation of breaking the blind should be recorded with the date/time and reason why the blind was broken, and the names of the personnel involved.

Emergency unblinding details are provided in the Pharmacy Manual.

The participant for whom the blind has been broken will be discontinued from the trial and undergo the ET procedures. In cases where there are ethical reasons to have the participant remain in the trial, the Investigator must obtain specific approval from the Sponsor or its designee for continuation. The primary reason for discontinuation (the event or condition which led to the unblinding) will be recorded.

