9.3.1. Efficacy Analyses

The aims of the analyses of the primary endpoint – percent change from baseline at Week 4 in 7-day average of daily peak pruritus NRS – is to test for treatment effect, to characterize the gel concentration-response curve, and to estimate the minimum effective and optimal concentration. The Multiple Comparison Modelling (MCPMod) approach will be applied to the analyses.

Candidate gel concentration-response models which will be used in the analysis include the following:

- Linear model.
- Quadratic model with maximum effect reached at 3.5%, the model parameter is -0.1428571.
- Exponential model which reaches 20% of the effects at 2.5%, the model parameter is 1.803368.
- E_{max} model with $ED_{50}=2.5\%$.
- Sigmoid E_{max} model with $ED_{50}=2.5\%$ and Hill's parameter = 2.5.

[figure not shown]
- Logistic model which reaches 20% and 95% effects at concentrations 2.5% and 5%, respectively, the model parameters are $ED_{50\%} = 3.3002654$, $\delta = 0.5772694$.

The minimum effective concentration is defined as the lowest concentration whose standardized effect size is at least 0.25 and is significantly different from placebo at a 2-sided significance level of 0.2.

The optimal concentration is defined as the highest concentration of ASN008 used in this clinical trial without safety concerns for linear and exponential models, or the lowest concentration which maintains 90% of the maximum effect for the rest of candidate models.

Figure 3 depicts the shapes of curves for each candidate model, assuming the vehicle effect is 10% and treatment effect is 40% (30% improvement over vehicle).

Figure 3 Candidate Concentration - Response Models

Analysis of primary endpoint consists of the following steps:

Mean and variance estimation: A Mixed model repeated measures with visit, treatment, baseline disease severity, and visit by treatment interactive and fixed effects, baseline NRS as covariate, participant as random effects will be fitted first, the least-squares means and their variance-covariance matrix at Week 4 will be estimated using the fitted model.

1. MCP-step: the candidate models are tested using the estimated means and their variance-covariance matrix from the previous step. If any of the models is statistically significant at

2-sided significance level of 0.1, the treatment effect is established, the analysis moves to the next step.

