### **4.2 Per-Protocol Set**

The Per-Protocol (PP) set includes all participants who were randomized, received at least 1 dose of study product without any major protocol deviations that may affect the efficacy outcome, received the treatment they were randomized to, who don't have missing baseline pruritus NRS, who don't have 50% or more missing pruritus NRS data in week 4. Those who discontinue the study treatment prior to NRS week 4 will also be excluded. The participants to be excluded from the per protocol set due to the major protocol deviations will be evaluated and determined prior to database lock by the sponsor.

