## **14.4 Electrocardiogram**

Descriptive statistics will be presented for data related to ECGs (heart rate, RR interval, PR interval, QRS duration, QT interval, and QTcF interval). Change from baseline values will be presented for each post-baseline assessment.

Shift tables from baseline to each post-baseline visit and to each timepoint describing shifts to abnormality will be provided for overall interpretation. Only participants with a baseline result and a result at the specified visit for the parameter will be considered.

A listing of ECG assessments will be provided. In addition, a listing will be provided for each parameter where a participant had at least 1 abnormal result.

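### The safety condition on the optimal concentration covers only two of the six candidate models, so the averaged optimum can exceed the highest concentration judged free of a safety concern

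*SAP*

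**What the plan says.** Protocol 9.3.1 and SAP 13.1 give the primary analysis three aims: to test for an effect, to describe the concentration-response curve, and to estimate the minimum effective and optimal concentrations.

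The optimal concentration has two definitions, depending on the model:

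- Linear and exponential: the "highest concentration of ASN008 used in this clinical trial without safety concerns for linear and exponential models".
- Quadratic, Emax, sigmoid Emax and logistic: "the lowest concentration which maintains 90% of the maximum effect for the rest of candidate models".

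In the last step, "weighted estimates for minimum effective concentration and optimal concentration will be calculated using weighing" over the models that passed the contrast test.

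Neither document says what counts as a safety concern for this purpose. The nearest text is in the Protocol Synopsis: "Any safety concerns arising during the study will be evaluated by the Medical Monitor and Sponsor to determine the appropriate course of action". That names the evaluators and concerns conduct of the trial. It gives no criterion and no link to the optimal concentration. Under Protocol 5.6, treatment codes are withheld from the Sponsor's "trial team until database lock is completed and all safety data has been cleaned and monitored".

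SAP Appendix 2 repeats the two-part definition and then gives one line of code, `ED(fit,0.9)`, with no safety input and no separate branch for the linear and exponential models.

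**The concern.** The plan treats safety as relevant to the optimum, since it says so for two models. It then averages those two with four models that ignore the same judgement. Followed exactly, the rule can declare 5% unacceptable and still report an optimum between 2.5% and 5%, a range in which no tested concentration was found free of concern.

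A second, smaller matter is timing. The Sponsor's trial team can compare safety between arms only once codes are released, and efficacy by arm is then available too. With no recorded criteria, the call on 5% could be made, or be seen to be made, with the efficacy curve in view. The reported optimum moves with that call.

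At stake is one Phase 2 output that is likely to inform the choice of concentration for later trials.

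**Working it through.** **Inputs.** Candidate models and guessed parameters from SAP 13.1; tested concentrations 0, 1.25, 2.5 and 5%.

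**Step 1: reproduce the plan's parameters.**
- Quadratic, peak at 3.5%: −1/(2 × 3.5) = −0.142857 (plan −0.1428571).
- Exponential, 20% of the effect at 2.5%: 1/(e^(2.5/δ) + 1) = 0.2, so δ = 2.5/ln 4 = 1.80337 (plan 1.803368).
- Logistic: δ = 2.5/(logit 0.95 − logit 0.20) = 2.5/4.3307 = 0.57727; ED50 = 2.5 + 0.57727 × 1.3863 = 3.30027 (plan 0.5772694 and 3.3002654).

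All agree.

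**Step 2: concentration giving 90% of the maximum effect on 0 to 5%.**

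| Model | Calculation | Result |
|---|---|---|
| Quadratic | 3.5 × (1 − √0.1) | 2.39% |
| Emax | effect at 5% is 0.667; 90% is 0.60; 0.60 × 2.5/0.40 | 3.75% |
| Sigmoid Emax (Hill 2.5) | effect at 5% is 0.850; 90% is 0.765; 2.5 × (0.765/0.235)^0.4 | 4.01% |
| Logistic | 3.3003 + 0.5773 × logit(0.8553) | 4.33% |
| Linear | 0.9 × 5 | 4.50% |
| Exponential | 1.803368 × ln(1 + 0.9 × 15) | 4.82% |

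The first four are the optima under the written rule. The last two are what `ED(fit,0.9)` returns for models whose written optimum is a tested concentration, so the code as shown does not follow the text for them. The maximum is taken over the tested range. Taken at the asymptote, Emax would give 2.5 × 9 = 22.5% and sigmoid Emax 2.5 × 9^0.4 = 6.02%, so the choice made here is the conservative one.

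**Step 3: average with equal weights (illustrative).** The four unconditioned optima sum to 2.393 + 3.750 + 4.007 + 4.326 = 14.476.
- No concern: (14.476 + 2 × 5)/6 = 4.08%.
- Concern at 5%, as written: (14.476 + 2 × 2.5)/6 = 3.25%.
- Concern at 5%, all six capped at 2.5%: (2.393 + 5 × 2.5)/6 = 2.48%.

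**Step 4: how often the conditioned models enter.** The contrast test was simulated at two-sided 0.1 with a maximum effect of 0.72 SD. Given a significant result, linear or exponential was among the significant models in 66% to 98% of trials at 24 per arm (70% to 99% at 30), depending on the true shape. They were the only significant models in 0.5% or fewer. The safety call therefore usually enters the average but almost never sets it alone.

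**Step 5: fitted models and data-driven weights.** Assumptions: 30 per arm, SD 40, a 28.8-point gain at the best tested concentration, refitted models, AIC weights over significant models, 3,000 trials per shape. Mean weighted optimum:

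| True shape | No concern | Concern at 5%, as written | Concern at 5%, capped |
|---|---|---|---|
| Linear | 4.31 | 3.02 | 2.45 |
| Quadratic | 2.57 | 2.21 | 2.04 |
| Exponential | 4.66 | 3.15 | 2.49 |
| Emax | 3.55 | 2.69 | 2.28 |
| Sigmoid Emax | 4.21 | 2.99 | 2.45 |
| Logistic | 4.65 | 3.14 | 2.50 |

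As written, with a concern at 5%, 35% (quadratic) to 99% (exponential, logistic) of significant trials still report more than 2.5%.

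**The case against.** The strongest reply is that the excess is small. With a concern at 5%, the mean weighted optimum in the simulation is 2.2% to 3.2%, and at least 99% of significant trials land nearer 2.5% than 5%. Only three strengths are manufactured, so a reader who rounds to the nearest would almost always choose 2.5%. This stands as to size. The plan states no rounding rule, however, and an estimate that breaches the plan's own condition still has to be explained.

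It can also be said that a concern at 5% does not show that 3% is unsafe. That is true, and it is why the uncapped value should be shown. But the plan already steps down to a tested concentration for two models and gives no reason to treat the other four differently.

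The code is labelled as sample code and follows the full definition, so it may simply be incomplete. The response description, covering participants "who do not use any prohibited medications during the entire study and have no safety concerns", is a loose summary; the operative missing-data rule does not use its safety phrase.

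Three stronger readings are tempting and are not supported:

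- *The undefined judgement decides the optimum.* It enters through two models of six and is averaged with the rest.
- *5% goes well beyond human experience, so a concern is likely.* Its rate (5% × 2 mg/cm² = 100 µg/cm²) is about twice the one repeated-dose rate given (about 49.2 µg/cm²). But Protocol 1.1 also cites negligible systemic exposure, tolerability and animal margins, has an unclear clause on rates already evaluated in Phase 1/1b, and does not give the Part A rates. The point does not need this argument.
- *Participants are unprotected.* Review by the Medical Monitor and Sponsor, withdrawal for adverse events (4.3), tolerability evaluation (8.1.6) and unblinding of individual cases (5.6, 8.2.7) are all provided.

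**Conclusion.** The inconsistency is real and minor. One safety condition is written for two models and omitted for four that enter the same average, so the reported optimum can exceed the highest tested concentration judged acceptable. With a concern at 5%, the equal-weight figure is 3.25% against 2.48% when capped. In simulation the gap between the rule as written and the capped rule is 0.17 points (quadratic truth) to 0.66 points (exponential truth). These sizes rest on the guessed shapes, an SD of 40, AIC weights and a maximum taken over 0 to 5%; real values will depend on the fitted models.

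The contrast test, its error rate, power and the estimated arm differences are unaffected. The missing definition of a safety concern would by itself be only a gap in detail. A reader might also infer that specific cut-offs or QTcF threshold counts are required. SAP 14.4 already gives QTcF change from baseline, shift tables "describing shifts to abnormality will be provided for overall interpretation" and listings of abnormal results, so further counts are a reporting preference.

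**What to change.** In SAP 13.1 and Appendix 2, before unblinding:

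1. Apply the same condition to all six models: cap each model's optimum, and hence the weighted estimate, at the highest tested concentration without a safety concern.
2. Report the uncapped weighted estimate beside it.
3. Give the linear and exponential models their own branch in the code, so that they return the tested concentration the text specifies rather than about 4.5% and 4.8%.
4. Have the Sponsor record which concentrations have a concern, and the criteria used, before efficacy results by arm are seen. The criteria are the Sponsor's to choose and should include local tolerability. The SAP already fixes a comparable decision in advance: per-protocol exclusions for major deviations "will be evaluated and determined prior to database lock by the sponsor".

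The cost is a short paragraph of SAP text and a few lines of code, with no new visit, sample or participant. Item 4 also needs safety by arm to be reviewed ahead of efficacy by arm. The downside is that a safety call made by chance would lower the reported optimum; showing the uncapped value lets the reader see by how much.
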